10. ETHICAL CONCERNS AND INFORMED CONSENT	
11. REFERENCES)
12. APPENDIX	2

Change	Rationale
Page 1 Indication that this is an amended	
protocol	
Protocol CFLD 002-R1	
Amendment #4: 11/11/2014	
Title Page [name] is now the PI at Johns Hopkins University; [name] and [name] are now the Project Official and Project Scientist; [name] replaced [name] as the lead statistician at the DCC; University of Washington (Seattle) and Anne & Robert H. Lurie Children's Hospital (Chicago)	Change of study PI at Johns Hopkins University; Change of project officials at NIDDK; and change of study statistician at the DCC. The network was expanded to 11 sites (Seattle and Chicago) to allow adequate recruitment of subjects with heterogeneous liver in a reasonable time frame.
were added as new sites with [name] MD and [name] MD as site PIs, respectively.	
Section 1 Changed study period from 5 years to 6 years; added text to clarify that study participants are age 3-12 years at the time of enrollment.	To allow for an additional ultrasound (US) visit in year 6; for clarification.
Section 2A #6-7 Eliminated references to five years of study follow up.	To allow for an additional year of follow up, which will include an additional US.
Section 4.1 Changed study period from 5 years to 6 years; added text to clarify that study participants are age 3-12 years at the time of enrollment.	To allow for an additional ultrasound (US) visit in year 6; for clarification.
Section 4.24 Eliminated references to five years of study follow up.	To allow for an additional year of follow up, which will include an additional US.
Section 4.3 Table 1 Changed "follow up visit" column from years 1-5 to years 1-6; changed "US visit" column to reflect the additional US at year 6.	To allow for an additional year of follow up, which will include an additional US in year 6.
Section 4.32 #7 Changed study period from 5 years to 6 years.	To allow for an additional ultrasound (US) visit in year 6.
Section 4.33 #11 Added text to indicate that elastography data will be collected locally as available; #12 Added text to include the ChiLDREN/ChiLDReN Network	Elastography data is being collected locally at sites that have the equipment. This may offer supplemental information. We will simply collect values and method (if performed locally) in addition to other clinical data we are already collecting; for clarification.

Details of Amendments in PUSH protocol

	1
Section 5 Changed study period from 5	To allow for an additional ultrasound (US)
years to 6 years.	visit in year 6.
Section 6.1 Added text to explain updated	We have modified the power and sample
sample size calculations and plans for	size calculations as the variability of US
analyses.	grading was shown to be larger than what
	has been expected prior to initiation of the
	study. To achieve a more reliable primary
	outcome, we extended the study period to 6
	years after screening US and introduced an
	interim analysis based on year 4 US results
	with a more stringent definition of
	development of cirrhosis.
Section 10 Changed study period from 5	To allow for an additional ultrasound (US)
years to 6 years and changed text to add a	visit in year 6.
fourth US in year 6.	
Section 10 Added text to address re-	To explain that the extension of the study
consenting of subjects who turn 18 during	to six years will result in some study
the course of the study.	subjects turning 18 during the course of
	their participation in the study. Those
	subjects will be asked to re-consent for
	themselves.
Section 12 Added University of	The network was expanded to 11 sites
Washington (Seattle) and Anne & Robert	(Seattle and Chicago) to allow adequate
H. Lurie Children's Hospital (Chicago) to	recruitment of subjects with heterogeneous
the list of participating centers; corrected	liver in a reasonable time frame;
the names of existing centers to reflect the	participating centers should be listed by the
names of the institutions that receive grant	name of the institution that receives the
awards, rather than hospital names.	grant funds for the study.

Change	Rationale
Page 1 Indication that this is an amended	
protocol	
Protocol CFLD 002-R1	
Amendment #3: 9/24/2013	
Page 16 Section 4.21 Inclusion Criteria	Correct measurement unit typo for Fecal
Corrected text for Fecal elastase	elastase from mg/gm to mcg/gm
to Fecal elastase <100 mcg/gm	

Change	Rationale
Page 1 Indication that this is an amended	This amended protocol includes study
protocol	followup for subjects found to have
Protocol CFLD 002-R1	cirrhosis or homogeneous liver on US;

Amendment #2: 5/30/2011	these subjects exited study in previous protocols.
Page 1: [name] is PI at Washington University; [name] is PI at Sick Kids in Toronto; [name] is PI at Baylor. Emory and Cincinnati have been added with [name] and [name], respectively, added as PIs. [name] was added to the list of Working Group	Change of study PI at Washington University and Hospital for Sick Children, Toronto. The network was expanded to 9 sites (Cincinnati and Emory) to allow adequate recruitment of subjects with heterogeneous liver.
members as the lead statistician. Page 10, Section 1: Objectives: Add text about following children who were not previously followed in this study; added text to clarify that children with known cirrhosis prior to screening are not eligible.	Study is being expanded to follow children who are found to have unsuspected cirrhosis or homogeneous liver on Screening US. Little is known about the progression or impact of early CF liver disease
Pages 11-12, Section 2: Modify hypothesis 4 to include homogeneous or cirrhosis echo pattern of the liver on abdominal US. Add hypothesis 6: Cirrhosis incidentally discovered on screening ultrasound does not progress to clinical evidence of portal hypertension during the 5 year study follow up. Add hypothesis 7: Homogeneous liver on	Add hypotheses regarding impact of cirrhosis or homogeneous liver on US on QOL/pulmonary function/nutrition. Add hypothesis on lack of progression of CF cirrhosis to portal HTN during the study period.
ultrasound does not progress to heterogeneous liver or cirrhosis during the 5 year study follow up.	Add hypothesis regarding lack of progression of homogeneous liver.
 Page 12, Section 2: Broaden specific aim 3 regarding impact of US findings on QOL, pulmonary function, and nutrition to include cirrhosis and homogeneous liver. Add specific aim 4 "To determine if Doppler velocity measurements of hepatic and splenic vessels predict an increased risk for the development of cirrhosis and to characterize these parameters and their progression in children with cirrhosis at screening" Add specific aim 5 to determine if cirrhosis on ultrasound progresses to portal hypertension during the study period Add specific aim 6 to determine if homogeneous liver progresses to either cirrhosis or heterogeneous liver. 	Specific aims are expanded to include cirrhosis and homogeneous liver at screening US impact on QOL/pulmonary function/nutrition, study of Doppler, progression of cirrhosis to portal HTN, progression of homogenous liver.
Page 15, Section 4.1: Add to Study Design	Design changed to follow children with

that children who are found to have unsuspected cirrhosis or a homogeneous liver pattern at screening ultrasound will be followed for 5 years to assess for the development of portal hypertension or cirrhosis and its progression.	cirrhotic or homogeneous liver pattern at screening US for the full 5 years of study.
Page 17, Section 4.23: Add text to clarify that we will now follow those children who are found to have cirrhosis or a homogeneous liver at screening US. Changed matching ratio. Heterogeneous subjects will now be matched to two normals for follow-up. Normals who had previously exited the study can be re- consented and followed as part of the new match ratio.	Design changed to follow children with cirrhotic or homogeneous liver pattern at screening US for the full 5 years of study. Matching ratio changed to address current rate of heterogeneous enrollment.
Page 17, Section 4.24: Number of participants: Groups clarified and expanded: A heterogeneous liver, B normal liver, C cirrhosis and D homogeneous. Increase enrollment number to 800 from 580. Decreased number of heterogeneous from 110 to 60 and edited text to reflect 60 matched trios instead of 110 matched pairs.	Subjects with cirrhotic and homogeneous pattern are retained in study (but not matched). Increase enrollment to meet target longitudinal enrollment of matched pairs and new groups to be followed. Updated enrollment totals by group per new matching ratio.
Page 17, Section 4.24: Enrollment procedures: add that subjects with cirrhosis or homogeneous liver will be followed for the study period.	Linked to new study aims.
Pages 17-18, Section 4.24: Re-contact and re-consent of previously exited homogenous and cirrhotic subjects, as well as normals who could now be matched into trios.	Allow these previously exited subjects the opportunity to be followed long term.
Page 18, Section 4.3: Clinical and lab evaluation: clarification that subjects with cirrhosis or homogeneous liver will be followed with yearly visits and biyearly US	Linked to new study aims.
Page 20, Section 4.32: Extend time requirement for completion of Screening US from 4 months to 7 months (also appears in Section 4.42). Added text clarifying that children with homogeneous patterns will be followed as Group D. Added text clarifying that all children with heterogeneous pattern will be followed, whether matched or not. Added text to	Allow for Screening US to be completed at either of next two scheduled CF clinic visits. Linked to new study aims.

clarify that Group B subjects' data will be	
maintained whether or not they are matched	
and followed.	
Pages 21-23, Section 4.33: Screening visit	Linked to new study aims.
and longitudinal visits changed to include	-
cirrhosis (group C) and homogeneous liver	
(group D)	
Page 22, Section 4.33: Added text to	Labs are not typically drawn at quarterly
clarify that lab data will typically be	CF visits. We have made an effort in this
collected at the subject's annual CF visit.	study to avoid additional blood draws and
5	
Labs for the longitudinal follow up visit	instead collect study labs and specimens
will be those collected at or after the	when they are also being drawn for the
longitudinal visit. Study specimens can be	annual CF visit.
collected at the time of the annual CF visit.	
Pages 25, Section 4.42: Removed text	Linked to new study aims. Per addition of
requiring a Grade of 0 or 1 upon entry into	two new study sites.
the study. Updated number of sites from 7	
to 9.	
Page 26, Section 4.42: Added text to	Study personnel may change over time.
clarify that new study radiologists will be	
trained per the process described.	
Page 28, Section 5: Termination or	Study will follow cirrhotic children until
Withdrawal: modified to state that subjects	completion unless they develop the
will be followed for 5 years unless they	endpoint of receiving a liver transplant.
receive a liver transplant, in which case	
they are terminated.	
Pages 28-29, Section 6.1: Added text to	Linked to new study aims.
explain sample size calculation changes and	
the change in the matching ratio. Updated	
enrollment targets and statistics to reflect	
new calculations.	
Pages 29-30, Section 6.2: Added and	Linked to new study aims.
-	Linked to new study anns.
updated text to correspond to new study	
aims.	
Page 1 Indication that this is an amended	
protocol	
Protocol CFLD 002-R1	
Amended 5/24/2009	
Amended 5/24/2007	
Page 2: Table of Contents added	
Page 8: All current and newly diagnosed	Toronto is not part of the CF Registry, but
patients (based on diagnostic and	has similar data in their registry.
enrollment criteria) with Cystic Fibrosis	the state of the test of the state of the st
aged 3 through 12 years of age who are	
aged 5 through 12 years of age who are	

enrolled in the CF Registry Study or the Toronto CF Registry, followed at each CFLD-NET Clinical Site will be offered enrollment into this study.	
Page 9 Inclusion criteria 1. Enrolled in the CF Registry Study or Toronto CF Registry	Addition of the Toronto CF Registry, as Toronto does not participate in the CF Registry (only US centers participate)
Page 9 Exclusion criteria Added: 1. Presence of Burkholderia cepacia	Burkholderia is very rare in the target population and analysis of data suggests that it will be nearly impossible to have an adequate match should a subject be identified with Burkholderia. Subjects who develop Burkholderia during the study will continue to be followed.
Page 10 Matching statement These study participants will be matched (one to one by age, center, gender, ethnicity and Pseudomonas aeruginosa status) to subjects from Group B (NL US).	Matching criteria were adjusted to eliminate race (minimal effect by analysis of preliminary data), Burkholderia (see item above) and genotype as all patients will be pancreatic insufficient
Page 10 duration of the study The study will continue to enroll patients until we accrue 110 matched pairs (HTG US and NL US). Thus recruitment of cases and controls will stop when 110 matched pairs are enrolled, our current best estimate for the sample screened is n=580	Based on the recommendation of the DSMB, we have clarified that the study will continue to enroll until we accrue 110 matched pairs. This may not be the case when we recruit the 110 th HTG US case.
Page 11: Clarification of follow up Follow Up: The Group A (HTG US) and a portion of Group B (NL US) subjects will be followed annually for 5 years or the development of cirrhosis (whichever comes first) as indicated below.	Once the subject develops cirrhosis, they will be at the endpoint of the study.
Page 11: Table: We have adjusted the Baseline visit name to Longitudinal Follow up visit 1 for clarity. Matching criteria data collection added to the screening visit and Diagnosis removed from the table	Change name of visit for clarity Data on matching is collected at the screening visit. Diagnosis confirmation is part of the eligibility criteria
 Page 12: we have clarified the data collected at the screening to meet matching criteria and NIH data collection: a. For Matching: DOB, Center, Gender, Ethnicity, pseudomonas status 	This clarifies the data collected for matching and collection of key data elements.

b. Other data: Race, CF Registry patient	
number, genotype (DeltaF508	
homozygous, heterozygous and other).	
Page 12 clarification of the matching strategy Group A (HTG US) subjects will be matched to a Group B subject (within 6 months of enrollment) and followed for up to 5 years. In the event that a match cannot be found for a Group A subject (HTG US) within six months of enrollment, the matching criteria will be relaxed sequentially using the algorithm specified in the MOO. All participants with a HTG US will be followed annually whether matched or not.	We have clarified the timing of the matching algorithm.
Page 13 Change Baseline Visit to Longitudinal Follow Up Visit 1	Visit name change for clarification
Page 13 Clarification of the timing of the	This visit is for patients who will be in
enrollment in the Longitudinal FU visit 1	longitudinal follow up. Matched Controls
for longitudinal followup This may be obtained any time after consent and after the entry US has been graded. It should occur within 3 months of determination that the subject is eligible for longitudinal follow up (Group 1 HTG US or a matched Control from Group 2 NL US)	may be more than 3 months from their US.
Page 14 Addition of the CFQ-R Preschool Version (3-6 years old)	Adding the preschool CFQ tool
Page 15 Numbering change 4.4 Specimens to be Collected	Correct a numbering issue
Page 16-17 Clarification that the Doppler	Clarification of the Doppler component of
measurements are a research component . The Doppler US will be the experimental arm of the study. US scans will be obtained after a minimum of a 4-hour fast for flow evaluation.	the US.
Liver echogenicity and contours will be assessed. Liver echogenicity will be evaluated by comparing it to that of the	

kidney. Irregularity or nodularity of the hepatic parenchyma and liver capsular surface, portal vein diameter, collateral vessel formation, ascites, and splenomegaly will be evaluated. Doppler US will be used to assess the presence and direction of flow in the main portal vein and right, main and left hepatic veins; and flow velocity will be assessed in the portal vein and resistive and pulsitility indices will be sought in the hepatic and splenic arteries.	
Page 17: Clarification that the radiologists will be blinded to results for the training set All 7 center radiologists who will be blinded to the results, will then grade the	Clarification that the radiologists will not know the results of the test sets.
liver ultrasound images. Page 17-18 Clarification of ongoing assessment of radiology readings Center radiologists must meet the accuracy cr outlined in the MOO before the study can stat any center.	Per the request of the DSMB we have outlined the ongoing quality assessment component for the radiologists.
The same training set used for the radiologists will be used to train the sonographers. In addition, there will be a written guide documenting the required images for the sonographers.	
There will be ongoing assessment of the quality of the US and the consistency of the US readings. The first five US studies from each institution will be reviewed by the lead radiologist (MS) to ensure uniform quality. A scoring sheet of the image quality for	
each of the first five US scans will be completed and stored at the data center and also sent to the radiologist at each institution. For each of the US images, there will be three readings of each image and assessment of the image quality (the center radiologist reading and 2 other readings).	

the radiologists in the study excluding the lead radiologist (MS). There will be ongoing assessment of discordance over time that will be tracked as a group and by individual radiologist as outlined in the MOO. We do anticipate some disagreement within one grade. All discordant readings will be reviewed by the lead radiologist (MS). Criteria for interventions are outlined in the MOO.	
 Page 20 Numbering clarification Primary Outcome is the development of cirrhosis Cirrhosis will be defined by imaging criteria (Grade 3 or 4 as described in 4.4 Section on US Grading) 	Number clarification
Page 20: Clarification of endpoints Subjects in the longitudinal follow up will be followed annually for up to 5 years or until they develop cirrhosis.	
Page 22: Addition to the risk statement Medical risks include those related to the identification of abnormalities or incidental findings on the abdominal ultrasound. These results will be discussed by the study investigators with the patient and family and the patient's care team with further management/referral directed by the care team.	Added to clarify the potential to identify other liver diseases.
Page 22 We have removed this statement: There is also a risk that the subject's US staging will be revealed as a result of the transport of US studies to the centers for re-reading. US studies will only contain a study ID with no PHI.	We have validated methods to have only a study ID

Prediction by Ultrasound of the Risk of Hepatic Cirrhosis in Cystic Fibrosis (PUSH)

1. OBJECTIVES

The primary objective of this prospective longitudinal study is to determine the utility of abdominal ultrasound (US) at enrollment to predict the development of cirrhosis in subjects with cystic fibrosis (CF) within approximately a six year period. This is a multi-center prospective longitudinal study of pancreatic insufficient children with CF who are enrolled at age 3 through 12 years. Subjects will be prospectively ascertained, enrolled and followed at yearly intervals for approximately six years, through the completion of the Year 6 US and study closeout procedures. This longitudinal study will involve the collection of clinical and outcome data at annual intervals for six years and standardized US at 2 year intervals, including Year 2, Year 4 and Year 6. The study will test the hypothesis that a heterogeneous echo pattern on ultrasound of the liver of children with CF will predict an increased risk for the development of cirrhosis. The development of the serum and urine repository, and the maintenance of a DNA bank or transformed cell lines for DNA analyses, will be an invaluable tool for current and future ancillary investigations into the pathogenesis of the development of cirrhosis in CF and the development of biomarkers and genetic markers that would be useful in identifying patients at risk of progression to cirrhosis. Data from this study will be stored and analyzed in a secure research database at the Data Coordinating Center (DCC), University of Michigan.

The study population will consist of individuals with cystic fibrosis, who are pancreatic insufficient, 3 through 12 years of age at time of enrollment and without known cirrhosis at the time of screening. In order to study the predictive ability of abdominal ultrasound, subjects will be followed for approximately six years, through the completion of the Year 6 US and study closeout procedures.

This study will:

- 1. collect detailed clinical and demographic information about each subject at enrollment and during follow up,
- 2. obtain and store imaging data from the subject at entry and during follow up,
- 3. obtain and store serum, plasma and urine samples from the subject at entry and during follow up,
- 4. obtain and store DNA from the subject,
- 5. obtain and store DNA from the biological parents,
- 6. obtain and store quality of life data from the subject and parents at enrollment and during follow up

Samples of serum, DNA, urine and imaging data will be stored in repositories for future research. The data and biological specimens may be used for detailed study into the mechanisms and causes of liver problems in subjects with CF and the risk of the development of cirrhosis in order to try to better diagnose and manage this condition. The subject will receive standard-of-care treatment and will not be restricted in type of treatment or from changes in treatment, such as newer treatments as they are developed.

The subjects may not directly benefit from participation in this research, but in the future other children and adults with similar problems may benefit from new information that may lead to better medical care.

Funded by the National Institute of Diabetes and Digestive and Kidney Diseases (NIDDK) and the Cystic Fibrosis Foundation (CFF), the Cystic Fibrosis Liver Disease Network (CFLD-NET) is governed by a Steering Committee comprised of the principal investigators from each of the participating clinical sites, the data coordinating center principal investigator, radiology core director, research coordinator representatives, CFF representatives and the NIDDK project scientists.

At the end of the clinical study, all unused biological specimens and data will be stripped of identifiers and will be kept in repositories under contract to NIDDK for future use by investigators who will gain access to them by way of a published review process.

2. HYPOTHESES AND SPECIFIC AIMS

The following hypotheses will be tested in this longitudinal study.

A. Hypotheses:

- 1. The finding of an isolated heterogeneous echo pattern in the liver on abdominal ultrasound (US) will predict an increased risk for the subsequent development of cirrhosis in children with cystic fibrosis.
- 2. There will be serum or plasma biomarkers that predict the development of cirrhosis in an individual.
- 3. There will be genetic modifiers that influence the development of cirrhosis.
- 4. There will be no effect on the quality of life, pulmonary or nutritional status of subjects by the finding of an isolated heterogeneous, homogeneous or cirrhosis echo pattern of the liver on abdominal US.
- 5. Doppler analysis of the hepatic and splenic vessels will be a better predictor than gray scale abdominal US alone to predict an increased risk for the subsequent development of cirrhosis
- 6. Cirrhosis incidentally discovered on screening ultrasound progresses slowly and does not result in complications of portal hypertension or hepatic synthetic failure during study follow up.
- 7. Homogeneous liver on ultrasound does not progress to heterogeneous liver or cirrhosis during study follow up.

These hypotheses will be tested by addressing the following Specific Aims.

B. Specific Aims:

The specific aims for this study are:

- 1. To determine if sonographic findings predict the risk of progression of liver disease to cirrhosis by comparing CF subjects with heterogeneous echogenicity pattern on US to those with normal echogenicity pattern on US
- 2. To develop a data and biorepository of serum, plasma, urine and DNA to aid the investigations in ascertaining the mechanisms, consequences, genetic risk factors and biomarkers for the development of cirrhosis
- 3. To determine if there are differences in health related quality of life, pulmonary or nutritional status in children with CF who have a heterogeneous, homogeneous or cirrhosis echo pattern on US compared to those who have a normal echo pattern on US
- 4. To determine if Doppler velocity measurements of hepatic and splenic vessels predict an increased risk for the development of cirrhosis and to characterize these parameters and their progression in children with cirrhosis at screening.
- 5. To determine if subjects with cirrhosis discovered in this study develop portal hypertension, complications of portal hypertension or worsening hepatic synthetic function during the study.
- 6. To determine if homogeneous ultrasound progresses to either heterogeneous ultrasound or cirrhosis during the study period.

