6. STATISTICAL CONSIDERATIONS

6.1 Sample Size and Power

The sample size calculations have been modified for Amendment 2 (date 5/30/2011). We have modified the calculations as the prevalence of heterogeneous US pattern in our study has not been as frequent as prior reports have suggested. Previous literature suggested a 15-20% prevalence of heterogeneous US in CF. In contrast, in this study, after 325 US studies, we have found a prevalence of 9%. Thus we have changed from matching heterogeneous US subjects 1:1 to 1:2. The sample size calculations have been further modified for Amendment 4 (11/11/2014). We have modified the calculations as the variability of US grading was shown to be larger than what has been expected prior to initiation of the study. To achieve a more reliable primary outcome, we extended the study period to 6 years after screening US and introduced an interim analysis based on year 4 US results with a more stringent definition of development of cirrhosis.

Characterizing the ability of US abnormalities to identify children at risk for progression to cirrhosis is the primary goal for this study. N =60 patients with heterogeneous livers will be compared with N = 120 patients with normal livers. Based on previous literature, in patients with a heterogeneous liver on US, 67% will progress to have US features consistent with cirrhosis and 46% will progress to portal hypertension (8). In patients

with a normal US, 7-13% will develop cirrhosis 5-7.5% will develop portal hypertension. Thus, patients with a heterogeneous liver have a 5.2 fold increased incidence of cirrhosis and a 6.1 fold increased incidence of portal hypertension compared to children with a normal US.

Based on the literature and our experience to date, we expect by Year 6 follow-up, 26% of HTGs and 8% of NLs will have converted to CIR. We will conduct an interim analysis when all longitudinal NL and HTG subjects have finished Year 4 US visit. To control for type I error with multiple tests, we consider p<0.025 to be statistically significant for both interim analysis and analysis at the end of the study.

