At Year 6 follow-up, group sample sizes of 60 and 120 achieve at least 80% power to detect a difference of 18% between the null hypothesis that both group proportions are 14% and the alternative hypothesis that the proportion in the heterogeneous liver (US) group is at least 26% using a two-sided chi-square test without continuity correction and with a significance level of 0.025. This corresponds to a relative risk of developing cirrhosis in the US group of 3.25 and an odds ratio of 3.9.

Preliminary analysis suggests that the US finding of CIR may be slightly more variable than we initially believed. Thus, when conducting the interim analysis, we will use a more stringent definition of development of cirrhosis: only cases graded as CIR with agreement among 3 or more radiologists (3/4 or 4/4) in the follow-up US visits will be considered as an event of converting to CIR in Group A (NL) and B (HTG). If the interim analysis shows significant difference between Group A and Group B, we will terminate the PUSH study.

With approximately 30 subjects in Group C (cirrhosis echo pattern on screening US) and 30 subjects in Group D (homogeneous echo pattern on screening US), the precision to estimate the incidence of portal hypertension or hepatic synthetic failure, and heterogeneous liver or cirrhosis, respectively, is provided in the table below.

Incidence Rate	Precision (Standard Error)		
0.05	0.040		
0.10	0.055		
0.15	0.065		
0.20	0.073		
0.25	0.079		

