For subjects in Groups C (cirrhosis on screening US) and D (homogeneous echogenicity on screening US), the analytic goal is estimation of the incidence of portal hypertension analysis of hepatic synthetic function, and the incidence of progression to heterogeneous liver or cirrhosis. Exact confidence intervals will be calculated.

Descriptive statistics will be provided for each of the secondary outcomes for the subjects in each of the groups defined by screening ultrasound: heterogeneous (Group A), normal (Group B), cirrhosis (Group C) and homogeneous (Group D).

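### Hypothesis 7 says homogeneous liver does not progress, but Group D progression is analysed with no reference rate, so Aim 6 cannot show whether a homogeneous scan carries excess risk

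*Protocol*

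**What the plan says.** Protocol Section 2 introduces its list with "The following hypotheses will be tested in this longitudinal study". Hypothesis 7 reads "Homogeneous liver on ultrasound does not progress to heterogeneous liver or cirrhosis during study follow up". It names no acceptable rate, margin or comparison group. The matching Aim 6 is "To determine if homogeneous ultrasound progresses to either heterogeneous ultrasound or cirrhosis during the study period", again about Group D alone.

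Section 6.1 provides for about "30 subjects in Group D (homogeneous echo pattern on screening US), the precision to estimate the incidence" as a table of standard errors, for incidences from 0.05 to 0.25. For Groups C and D, Section 6.2 says that "the analytic goal is estimation of the incidence of portal hypertension", followed by hepatic synthetic function and progression to heterogeneous liver or cirrhosis, with exact confidence intervals. The chi-square, logistic and Cox analyses of cirrhosis in Section 6.2 compare Groups A and B only. Aim 3 does set homogeneous against normal, but only for quality of life, pulmonary and nutritional status.

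On normal livers, Section 6.1 states "we expect by Year 6 follow-up, 26% of HTGs and 8% of NLs will have converted to CIR" and cites literature in which, among patients "with a normal US, 7-13% will develop cirrhosis".

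**The concern.** The hypothesis is absolute, yet the protocol does not expect even normal livers to be free of progression. A homogeneous pattern that behaved exactly like a normal one would still yield some conversions, so a non-zero count in Group D says nothing by itself about the homogeneous pattern. A zero count in about 30 children is also weak evidence of safety.

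Aim 6 is useful if it tells clinicians whether a homogeneous scan is more worrying than a normal one. That question needs the normal-liver rate beside the Group D rate. About 120 Group B children are followed with the same ultrasound process, but Section 6.2 does not use them for this outcome.

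**Working it through.** **Inputs.** Group D size 30 (Sections 4.24 and 6.1). Normal-liver conversion to cirrhosis by Year 6: 8% (Section 6.1). Literature range 7–13% (Section 6.1; Section 3.1 ties that study to an average of 10 years of follow-up, so it serves here only as a sensitivity range). Followed Group B: 120. Assumptions not stated in the protocol: a two-sided 95% level for the exact intervals, and no dropout.

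**1. The plan's own figures.** SE = √(p(1−p)/30) gives 0.0398, 0.0548, 0.0652, 0.0730 and 0.0791 at p = 0.05, 0.10, 0.15, 0.20 and 0.25. All five entries in the Section 6.1 table reproduce.

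**2. Chance of at least one cirrhosis conversion if Group D behaves like normal livers.** P(≥1) = 1 − (1−p)^30.
- p = 7%: 1 − 0.93^30 = 88.7%
- p = 8%: 1 − 0.92^30 = 91.8%
- p = 13%: 1 − 0.87^30 = 98.5%

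The expected count at 8% is 30 × 0.08 = 2.4. Hypothesis 7 also counts conversion to heterogeneous, for which the protocol gives no normal-liver rate. On the combined endpoint the rate can only be equal or higher, so at the 8% assumption with 30 fully followed, 91.8% is a floor. Section 6.1 also reports more grading variability than expected, which could add apparent conversions.

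**3. What a zero count shows.** The exact 95% upper limit for 0/30 is 1 − 0.025^(1/30) = 11.6%, which is above 8%. If the true rate were 8%, zero events would still occur with probability 0.92^30 = 8.2%. For zero events to exclude 8%, n must be at least ln(0.025)/ln(0.92) = 44.2, so 45 children.

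**4. Small non-zero counts.** Exact 95% intervals are 0.1–17.2% for 1/30, 0.8–22.1% for 2/30 and 2.1–26.5% for 3/30. All contain 8%.

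**5. Sensitivity to dropout.** With an assumed 20% loss (24 evaluable), step 2 at 8% becomes 1 − 0.92^24 = 86.5%, and the step 3 limit becomes 1 − 0.025^(1/24) = 14.2%. The conclusion is the same.

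**6. What a comparison with Group B would give.** With both groups at 8%, the large-sample 95% half-width for D minus B is 1.96 × √(0.08 × 0.92 × (1/30 + 1/120)) = 1.96 × 0.0554 = 10.9 points. Expected cirrhosis events are 2.4 in D and 120 × 0.08 = 9.6 in B, 12 in all. An interval of about ±11 points around zero would exclude an excess as large as the one the protocol expects for heterogeneous livers (26 − 8 = 18 points), but not a modest one.

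**The case against.** The strongest reply is that Section 6.2 makes estimation the goal for Group D and plans exact intervals. Zero of 30 would then be reported with an upper limit near 11.6%, and 2 of 30 as 0.8–22.1%, so the uncertainty would be visible. That stands.

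A reader might infer that one conversion refutes Hypothesis 7 and that none confirms it. No section says so. The 92% is the consequence of taking the wording literally, not of a written decision rule. A reader might also infer that the standard-error table is wrong or conceals something. It is correct for n = 30 and labelled as standard errors, and Section 6.2 builds exact intervals, not intervals from that table.

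It can further be said that a comparator for a secondary outcome may sit in a statistical analysis plan that is not at hand, and that Aim 6 literally asks only whether progression occurs. The first part is fair as to detail. But the absolute hypothesis, its status as something to be tested and the one-group goal are all fixed in the protocol, and they sit badly with the protocol's own 8%. As to the second, a bare yes to whether progression occurs is close to certain in advance and therefore tells little.

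Finally, a Group D versus Group B contrast has real limits. Its interval is wide. About 12 expected cirrhosis events cannot support adjustment for 11 centers. Group B was matched to Group A on age, center and *Pseudomonas* status, not to Group D. These points shape the fix but do not remove the need for a reference rate.

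**Conclusion.** The point holds in limited form. Hypothesis 7 is stated absolutely and listed as to be tested, while the planned analysis supplies no reference rate. At the protocol's own 8%, a Group D with no excess risk would show at least one cirrhosis conversion about 92% of the time, and zero conversions would not exclude 8%. Neither outcome shows whether a homogeneous pattern carries excess risk.

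These figures rest on 30 children with complete follow-up, Group D behaving like Group B, and a 95% level. The one-group exact interval is legitimate and should stay; the fault lies in pairing it with that hypothesis. This is a secondary aim, and the primary comparison of Groups A and B is not affected.

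**What to change.** - **Hypothesis 7 and Aim 6:** restate as progression in homogeneous livers being no more frequent than in normal livers.
- **Section 6.2:** keep the exact one-group interval. Add the Group D minus followed Group B difference in cumulative incidence with a 95% confidence interval, for cirrhosis and separately for heterogeneous-or-cirrhosis.
- **Method:** make the unadjusted score or exact interval the main result, with an age-adjusted sensitivity analysis only. State that Group B was matched to Group A and not to Group D.
- **Interpretation:** judge by the upper confidence limit, not by absence of events or a non-significant test. Report the aim as inconclusive if that limit still allows a relevant excess.
- **Time horizon:** Section 4.24 gives 5 years of follow-up for Group D, and Section 4.1 gives approximately six. These must be reconciled so that both groups are compared over the same period.
- **Optional, Section 6.1:** state that 0/30 has an exact 95% upper limit of 11.6%.

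The cost is rewording one hypothesis and one aim, and adding one comparison that uses followed groups and scans already planned. The downside is the half-width of about 11 points at 8%: Aim 6 may remain inconclusive, and the protocol should say so in advance.
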